APPENDIX 4: SAMPLING OF HOUSEHOLD CONTACTS

This addendum is applicable to household contacts of long-term shedders in this phase 2 study with nOPV2 vaccine candidates. (Long-term shedders are defined as subjects in this phase 2 study with at least one PCR-positive stool sample after Day 42 following last study vaccination). A subject will be considered to have completed the study if he or she has completed all study related procedures 42 days after the last study vaccination and shedding is PCR-negative on 3 consecutive stool samples (with a maximum of one sample per day).

If type 2 virus shedding is detected by PCR on one of the last 3 scheduled stool samples, the study duration for this individual will be extended. As soon as these results are known (anticipated 3 weeks after the last such sample provided for evaluation) the subject will be asked to further collect 3 consecutive stool samples (with a maximum of one sample per day) after the last per-protocol sample, and to repeat this until shedding is PCR-negative for type 2 poliovirus on 3 consecutive stool samples.

As an additional risk assessment measure, household contact monitoring will be offered in case of extended shedding (PCR-positivity of at least one of the follow-up stool samples after D42 following last study vaccination).

Procedure:

In case of extended shedding subjects will be asked to contact their household members with the request that at least one of them volunteers to collect 3 consecutive stool samples and to repeat this until the long-term shedder reaches end of shedding (PCR negative on 3 consecutive stool samples).

Informed consent forms will be distributed by the long-term shedders to their household contacts, sampling material will be made available once the household contact has signed the ICF, and appointments will be made with the study team;

Households are defined as contacts of the original study participant living under the same roof for a minimum period of one day post vaccination and being older than 18 years of age.

If a stool sample of a household member is PCR-positive, risk mitigation measures, such as the use of enhanced hygiene techniques and/or chemical toilets will be offered, and the procedure may be expanded to other household contacts subject to their consent.

Viral shedding assessment:

Collected stools will be analyzed by methods similar to the clinical study UAM4. In brief, stool samples will be shipped in batches to the C.D.C. (U.S.) for analysis by PCR. The method employed allows the identification and discrimination of each candidate from the other and from Sabin OPV2. If the samples are determined to be positive for either candidate vaccine virus, the virus titer may be measured in cell culture as a 50%

infectious dose (CCID₅₀). For samples with sufficient titer (e.g. >4.00 log CCID₅₀ per gram of stool) or if otherwise assessed to be important based on public health considerations, sequencing may be conducted in order to examine the preservation of the attenuating features of the nOPV2 candidate, particularly the retention of the modified, attenuated domain V region. Assessment of the neurovirulence of culture-amplified shed virus using a transgenic mouse assay is not anticipated; however, such testing would be considered in the event of unexpected clinical or sequencing observations.

1.1 Abbreviations

AE	Adverse event
bOPV	Bivalent oral poliovirus vaccine
bpm	Beats per minute
CCID ₅₀	50% cell culture infective dose
CI	Confidence interval
CRF	Case Report Form
CTCAE	Common Terminology Criteria for Adverse Events
cVDPVs	Circulating vaccine-derived polioviruses
cVDVP2	Circulating vaccine-derived poliovirus type 2
DBP	Diastolic blood pressure
DNA	Deoxyribonucleic acid
eCRF	Electronic Case Report Form
EDC	Electronic Data Capture
GCP	Good Clinical Practice
GMT	Geometric mean titer
GPEI	Global Polio Eradication Initiative
HBsAg	Hepatitis B surface antigen
HCV	Hepatitis C virus
HIV	Human immunodeficiency virus
HR	Heart rate
ICF	Informed Consent Form
ICH	International Conference on Harmonization
IEC	Independent Ethics Committee
IME	Important medical event
IMP	Investigational medicinal product
IPV	Inactivated poliovirus vaccine
IRB	Institutional Review Board
LSLV	Last Subject Last Visit
MedDRA	Medical Dictionary for Regulatory Activities
mOPV2	Monovalent oral poliovirus vaccine type 2
nOPV2	Novel oral poliovirus vaccine type 2
OPV	Oral poliovirus vaccine
PD ₅₀	50% paralytic dose
PP	Per-protocol
RNA	Ribonucleic acid
SAE	Serious adverse event
SAGE	Strategic Advisory Group of Experts on immunization
SAP	Statistical Analysis Plan
SBP	Systolic blood pressure
SD	Standard deviation

SmPC	Summary of Product Characteristics
SUSAR	Suspected Unexpected Serious Adverse Reaction
TgPVR	Transgenic mice expressing the cell receptor for poliovirus
TMF	Trial Master File
tOPV	Trivalent oral polio vaccine
VAPP	Vaccine-associated paralytic poliomyelitis
WHO	World Health Organization
WPV	Wild poliovirus

2 Introduction

This document outlines the statistical methods to be implemented for the analysis of the data resulting from Protocol UAM4, *A Phase 2, partial blind, randomized, placebo-controlled, multicenter study to evaluate the safety and immunogenicity of two novel live attenuated serotype 2 oral poliovirus vaccines candidates, in healthy adults previously vaccinated with oral polio vaccine (OPV) or inactivated polio vaccine (IPV), compared with historical controls given Sabin OPV2 or placebo*. Results of the proposed analyses will be used in the clinical study report for this protocol.

The purpose of this statistical analysis plan (SAP) is to provide specific guidelines for all statistical analyses. All analyses specified in this document will be performed. Any changes will either be reflected in amendments to this plan before the database lock or documented in the final statistical and clinical study reports. Other analyses that are not included in the SAP may be specified subsequent to its finalization. Such analyses will be described in an addendum as post-hoc and exploratory to the finalized SAP and will be performed if agreed among the participating institutions.

3 Study Overview

3.1 Background and rationale

This is a Phase 2 study of the safety and immunogenicity of two novel attenuated serotype 2 oral poliovirus vaccines given to adults with either an inactivated polio vaccine (IPV) background, or a live oral polio vaccine (OPV) background. Its purpose is to provide safety, immunogenicity, and stool viral shedding data that will support continued clinical development in younger age groups, targeted at licensure of a new type 2 oral poliovirus vaccine, as the serotype 2 Sabin strain oral poliovirus vaccine has been removed from routine immunization strategies worldwide.

3.2 Study design

This is a multicenter, partial blind, placebo-controlled, randomized study in 200 healthy OPV-vaccinated adults and in 48 to 132 healthy IPV-only vaccinated adults (age range 18 to 50 years), as follows:

- 50 OPV-vaccinated adults to receive 1 dose of nOPV2 candidate 1 (Group 1);
- 50 OPV-vaccinated adults to receive 2 doses of nOPV2 candidate 1 (Group 2), administered 28 days apart;
- 50 OPV-vaccinated adults to receive 1 dose of nOPV2 candidate 2 (Group 3);

- 50 OPV-vaccinated adults to receive 2 doses of nOPV2 candidate 2 (Group 4), administered 28 days apart;
- 16 to 44 IPV-only vaccinated adults to receive 2 doses of nOPV2 candidate 1 (Group 5), administered 28 days apart;
- 16 to 44 IPV-only vaccinated adults to receive 2 doses of nOPV2 candidate 2 (Group 6), administered 28 days apart;
- 16 to 44 IPV-only vaccinated adults to receive placebo (Group 7), administered 28 days apart.

3.3 Schema

Error! Reference source not found. provides a summary of the study groups and vaccines administered, including background vaccination, number of doses, and sample size.

Study code/ Nº Country	Group	Age (yr)	Immunogenic Background	Candidate	Study Cohort Size	No. of Doses	Dose level
UAM4 Belgium	Group 1	18-50	OPV	nOPV2 candidate 1	50	1	$\sim 10^6$
UAM4 Belgium	Group 2	18-50	OPV	nOPV2 candidate 1	50	2	$\sim 10^6$
UAM4 Belgium	Group 3	18-50	OPV	nOPV2 candidate 2	50	1	$\sim 10^6$
UAM4 Belgium	Group 4	18-50	OPV	nOPV2 candidate 2	50	2	$\sim 10^6$
UAM4 Belgium	Group 5	18-50	IPV	nOPV2 candidate 1	16-44	2	$\sim 10^6$
UAM4 Belgium	Group 6	18-50	IPV	nOPV2 candidate 2	16-44	2	$\sim 10^6$
UAM4 Belgium	Group 7	18-50	IPV	Placebo	16-44	2	Sirupus simplex

Table 1. Study Schema

3.4 Study objectives

3.4.1 Primary objective

The primary objectives of the study are

- To assess the safety (serious adverse events [SAEs] and severe adverse events [AEs]) of novel monovalent live attenuated oral serotype 2 poliovirus vaccine (nOPV2) candidate 1 and novel monovalent live attenuated oral serotype 2 poliovirus vaccine (nOPV2) candidate 2 in healthy OPV-vaccinated adults, relative to historical controls given Sabin OPV2 (study UAM1);
- To compare the immunogenicity (seroprotection rate) of novel monovalent live attenuated oral serotype 2 poliovirus vaccine (nOPV2) candidate 1 and novel monovalent live attenuated oral serotype 2 poliovirus vaccine (nOPV2) candidate 2 in healthy OPV-vaccinated adults to historical controls given Sabin OPV2 (study UAM1);
 - **Seroprotection** is defined as type 2-specific neutralizing antibody titers $\geq 1:8$ and seroprotection rate as the percentage of seroprotected subjects per group.
- To assess the safety (serious adverse events [SAEs] and severe adverse events [AEs]) of nOPV2 candidate 1 and nOPV2 candidate 2 in healthy IPV-only vaccinated adults, compared with placebo.

3.4.2 Secondary objectives

Secondary objectives are

- To assess the safety (any solicited and unsolicited AEs, laboratory assessments) of nOPV2 candidate 1 and nOPV2 candidate 2 in healthy OPV-vaccinated adults, compared with historical controls given Sabin OPV2 (study UAM1);
- To assess the safety (any solicited and unsolicited AEs, laboratory assessments) of nOPV2 candidate 1 and nOPV2 candidate 2 in healthy IPV-only vaccinated adults, compared with placebo;
- To compare the immunogenicity (seroconversion rate, median antibody titer (post-vaccination)) of nOPV2 candidate 1 and nOPV2 candidate 2 in healthy OPV-vaccinated adults, with historical control of Sabin OPV2 (study UAM1);
 - **Seroconversion** is defined as a change from seronegative to seropositive and neutralizing antibody titers of $\geq 1:8$, and in seropositive subjects, as an antibody titer increase of ≥ 4 fold over baseline titers.
- To assess the immunogenicity (seroprotection rate, seroconversion rate, median post-vaccination antibody titer) of nOPV2 candidate 1 and nOPV2 candidate 2 in healthy IPV-only vaccinated adults.

3.4.3 Exploratory objectives

Exploratory objectives are

- to compare immunogenicity (geometric mean titer [GMT]) of nOPV2 candidate 1 and nOPV2 candidate 2 in healthy OPV-vaccinated adults, with historical control of Sabin OPV2 (study UAM1);
- to assess immunogenicity (geometric mean titer [GMT]) of nOPV2 candidate 1 and nOPV2 candidate 2 in healthy IPV-only vaccinated adults;
- to compare viral shedding following nOPV2 candidate 1 or nOPV2 candidate 2 administration in a pre-specified subset of stool samples in healthy OPV-vaccinated adults, with historical control of Sabin OPV2 (study UAM1);
- to assess viral shedding following nOPV2 candidate 1 or nOPV2 candidate 2 administration in a pre-specified subset of stool samples in healthy IPV-only vaccinated adults;

The shedding analyses may initially be conducted using a subset of samples in the 10 days following administration of each dose (e.g. day 0, 3, 5, 7, and 10) and all samples at day 14 and thereafter. The remaining samples will be stored pending evaluation of the initial analyses; PCR and CCID₅₀ will be conducted on these stored samples if deemed important for the complete interpretation of the study results.

Exploratory objectives will also include comparison of neurovirulence (as measured in animal model(s)) and assessment of the genetic stability via analysis of genetic sequence, including but not limited to the modified regions of shed virus in a subset of stool samples of all OPV-vaccinated adults, relative to historical control of Sabin OPV2.

Exploratory objectives will also include assessment of neurovirulence (as measured in animal model(s)) and the genetic stability via analysis of genetic sequence, including but not limited to the modified regions of shed virus in a subset of stool samples of all IPV-only vaccinated adults given doses of nOPV2 candidates 1 and 2.

3.5 Study endpoints

3.5.1 Primary endpoints

Safety: The following endpoints will be evaluated by group and overall:

- incidence, type and causality of SAEs and severe AEs throughout the study period.

Immunogenicity:

- seroprotection rate of type 2 polio antibodies at Day 28, following a single dose of nOPV2 candidate 1 (combined Groups 1 and 2).
- seroprotection rate of type 2 polio antibodies at Day 28, following a single dose of nOPV2 candidate 2 (combined Groups 3 and 4).

Seroprotection is defined as type 2-specific neutralizing antibody titers $\geq 1:8$.

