- 18. Subject is an employee of the Investigator or study site, with direct involvement in the proposed study or other studies under the direction of that Investigator or study site, or is a family member of an employee or the Investigator, or was a study subject in the historical control studies UAM1 or UAT1 or in the study UAM4a;
- 19. Having a family or household member participating in the study CVIA 065 or being a study subject in the study CVIA 065.

Test Product and Placebo, Dose, Mode of Administration:

nOPV2 candidate 1 and nOPV2 candidate 2 are attenuated serotype 2 polioviruses derived from a modified Sabin 2 infectious clone and propagated in Vero cells.

Each dose of nOPV2 candidate 1 and nOPV2 candidate 2 contains approximately 10^6 50% cell culture infective dose units (CCID₅₀).

Sirupus simplex, Propylenglycolum, European Pharmacopoeia (Ph.Eur.), will be used as placebo. This clear, colorless to pale yellow liquid contains 64% saccharose, 0,08% methylparaben, 0,02% propylparaben and propyleneglycol, presented in a HDPE container of 1 liter.

The vaccines and placebo will be administered orally. One dose of vaccine (0.3 ml) is contained in six drops which are delivered with a spoon from the dropper supplied with the vaccine. For the placebo a pipette will be used to count 6 drops on a spoon to be administered in a similar way to the subject.

Reception of the vaccines, dose preparation and administration will be done by unblinded medical study personnel who will not participate in any safety evaluation.

Study/Treatment Duration:

Study duration is expected to be 6 weeks for subjects receiving 1 dose and approximately 10 weeks for subjects receiving 2 doses, including the 6-week safety follow-up period after last administration.

However, if any AE or SAE, including clinically significant abnormalities in laboratory safety testing are observed subjects will continue to be followed until these are resolved or determined to be chronic or stable or until the event is otherwise explained.

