Also, if type 2 virus shedding is detected by PCR on one of the last 3 scheduled stool samples, the study duration for this individual will be extended. As soon as these results are known (anticipated approximately 3 weeks after the last such sample provided for evaluation) the subject will be asked to collect further 3 consecutive stool samples (with a maximum of one sample per day) after the last per-protocol sample, and to repeat this until shedding is PCR-negative for type 2 poliovirus on 3 consecutive stool samples, which then determines study end for this person.

If the last stool sample is missing the subject will be asked to provide a new sample as soon as possible in order to determine their end of study or the need for further stool sample collection according to the collection cadence until shedding is PCR negative on 3 consecutive stool samples.

[†] Updated list will be made available at the start of the study. Study will take in consideration the most recent WHO guidelines.

Criteria for Evaluation:

Assessment of the following endpoints for the 2 candidate vaccines in OPV primed subjects (Groups 1 to 4) will be based on comparison with data obtained in the previously conducted Phase 4 study of Sabin mOPV2 in order to assess immunogenicity and establish an acceptable safety profile in these populations. For the safety endpoint of the IPV-primed subjects (Groups 5, 6) comparison will be made with the data of the placebo group (Group 7).

Primary

Safety: The following endpoints will be evaluated **by group and overall:**

- incidence, type and causality of SAEs and severe AEs throughout the study period.

Immunogenicity:

- seroprotection rate of type 2 polio antibodies at Day 28, following a single dose of nOPV2 candidate 1 (combined Groups 1 and 2).
- seroprotection rate of type 2 polio antibodies at Day 28, following a single dose of nOPV2 candidate 2 (combined Groups 3 and 4).
- Seroprotection is defined as type 2-specific antibody titers $\geq 1:8$.

Secondary

Safety: The following endpoints will be evaluated **by group and overall:**

- incidence, type, causality and severity of solicited adverse events for days 0-7 in Groups 1 and 2 combined and days 28-35 in Group 2;
- incidence, type, causality and severity of solicited adverse events for days 0-7 in Groups 3 and 4 combined and days 28-35 in Group 4;
- incidence, type, causality and severity of solicited adverse events for days 0-7 and days 28-35 in Groups 5, 6 and 7;

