6.6 RANDOMIZATION AND BLINDING

All OPV-vaccinated subjects will receive one of the nOPV2 candidates in a single blind manner and all IPV- vaccinated subjects will receive one of the nOPV2 candidates or placebo in a double-blinded manner.

For the whole study duration all subjects and blinded study staff responsible for safety evaluation of IPV-subjects will not have any information of what has been administered. As the placebo can be distinguished from the vaccine candidates in packaging and color, reception of the vaccines, dose preparation and administration will have to be done by a team of unblinded study personnel. Appropriate measures will be taken at the site to ensure blinding of subjects and blinded team for the whole duration of the study.

Groups will be enrolled sequentially such that subjects receiving candidate 2 will be enrolled first (IPV and OPV groups simultaneously), followed by subjects receiving candidate 1. IPV-only vaccinated adults will be randomized 2:1 to candidate 2 (Group 6) or placebo (Group 7), respectively, until all **16 to 44** Group 6 subjects are enrolled, after which randomization 2:1 to candidate 1 or placebo will commence for Groups 5 and 7. For OPV-vaccinated subjects, randomization to Groups 1 and 2 to receive candidate 1 will ensue following complete randomized enrollment of subjects to Groups 3 and 4. In all cases, block randomization will be used to ensure balanced randomization across time. The target will be to enroll 200 eligible OPV-vaccinated subjects and **48 to 132** eligible IPV-only vaccinated subjects. **The DSMB has established stopping rules for safety prior to study start which will be continuously assessed. The DSMB will also monitor study enrollment, particularly for IPV-vaccinated subjects, and recommend truncation and/or closure of study groups if enrollment stagnates and when current enrollment is considered sufficient to meet study objectives and no safety signals occurred. The minimum number of IPV-vaccinated subjects agreed on by DSMB per vaccine candidate is 24. With a randomization of 2:1 for placebo the minimum study cohort size for Groups 5, 6 and 7 will be 16. In case of safety signals the DSMB reserves the right to reverse the truncated enrollment.**

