- l. Subjects will be asked to collect the first stool of every day in the provided container and to store this in the provided thermal bag with cooling elements: after each vaccine dose, daily collection on Days 0 to 10 plus collection on Days 14, 21, V4 minus 1 or 2 days (= V7 minus 1 or 2 days after 2nd vaccination) and V8 minus 1 or 2 days. At Day 0, the storage procedure will be explained and the collection material provided. Subjects who are still shedding virus in one of the 3 last stool samples will be asked to further collect 3 consecutive stool samples every 3 weeks till end of shedding.
- m. Remote contact (text message by sms, WhatsApp or email) on Day 3 and on Days 21, 31 and 49 for safety follow-up and reminder stool collection scheme.
- n. Adverse events and intake of concomitant medication(s) will be monitored continuously from informed consent until the last study-related activity. The subjects can record unsolicited AEs on their diary card.
- o. After signing on screening visit, weekly reminder Code of Conduct by email or sms and on each visit to emphasize the need and importance of hygienic measures and respecting the inclusion/exclusion criteria until end of study.

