8.2 IMMUNOGENICITY

8.2.1 *Immunogenicity Variables*

Neutralizing Type 2 Poliovirus Antibody Titers

Blood samples for the determination of neutralizing type 2 poliovirus antibodies will be taken at the time points specified in the Time and Events schedule.

Neutralizing antibodies against type 2 poliovirus will be determined using a sero-neutralization assay.

Detailed descriptions of the collection, handling, transport and processing of the blood samples will be included in the laboratory manual.

Viral Shedding

Stool samples will be collected at the time points outlined in the Time and Events schedule.

As a measure of intestinal immunity, shedding of type 2 poliovirus in the stools will be evaluated using:

- Quantitative PCR (viral identity).
- CCID₅₀ determination (titer).

The shedding analyses will initially be conducted using a subset of samples in the 10 days following administration of each dose (e.g. day 0, 3, 7, and 10) and all samples at day 14 and thereafter. The remaining samples will be stored pending evaluation of the initial analyses; PCR and CCID₅₀ will be conducted on these stored samples if deemed important for the complete interpretation of the study results.

Shedding results for last stool sample will be provided to the sites in a timely manner in order to inform subjects about the need for further stool sampling every 3 weeks and taking precautions.

Detailed descriptions of the collection, handling, transport and processing of the stool samples will be included in the laboratory manual.

8.2.2 *Immunogenicity Criteria*

For an overview of endpoints, see Section 3.

The following endpoints will be based on neutralizing type 2 poliovirus antibody titers:

- Seroprotection: poliovirus type 2-specific titers $\geq 1:8$;
- Seroconversion: a change from seronegative to seropositive and antibody titers of $\geq 1:8$, and in seropositive subjects, as an antibody titer increase of ≥ 4 fold over baseline titers;
- Median titer and GMT 28 days post-vaccination and 56 days post-vaccination for Groups 2, 4, 5 and 6.

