8.3 SAFETY EVALUATIONS

The safety assessment in this study will be based on AEs, clinical laboratory tests, vital signs, and physical examination, as described in the following sections.

8.3.1 *Adverse Events*

Adverse events will be monitored continuously from informed consent until the last study-related activity. At regular intervals during the study, subjects will be asked non-leading questions to determine the occurrence of any AEs. All AEs reported spontaneously during the course of the study will be recorded as well.

For detailed definitions and reporting procedures of AEs, see Section 11.

Solicited AEs will be recorded for 7 days following each vaccine dose using a Diary Card.

8.3.2 *Clinical Laboratory Tests*

Blood samples of about 15 mL will be collected at the time points indicated in the Time and Events schedule.

Biochemistry and hematology testing will be performed on these samples, as well as serology testing (HBsAg, anti-HCV, anti-HIV antibodies, and total serum IgA) on the sample from Day 0. In female subjects of childbearing potential, also urine β -human chorionic gonadotropin (hCG) will be tested at Day 0 and at last visit in each group and at Day 28 in Groups 2, 4, 5, 6 and 7.

Standard laboratory tests as outlined in Appendix 1 will be performed by the local laboratory.

The Investigator must review the laboratory report, document this review, and record any change occurring during the study he/she considers to be clinically relevant in the source documents and in the AE section of the eCRF. Laboratory values outside the normal range will be flagged and their clinical relevance and causality will be assessed by the Investigator. A copy of all laboratory reports must be filed in the subject's medical records.

Samples that remain after protocol-specific assessments have been performed may be used for further exploratory work on polio. No human DNA or RNA analysis will be performed.

8.3.3 *Vital Signs*

Vital sign parameters will be assessed after 5 minutes in supine position at the time points indicated in the Time and Events schedule.

The vital sign parameters that will be assessed are supine systolic and diastolic blood pressure (SBP and DBP, respectively), pulse rate and oral body temperature.

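### The unsolicited SAE and severe-AE comparisons of Groups 5 and 6 with placebo have no closing day, so vaccinees extended for shedding are followed longer

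*SAP*

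**What the plan says.** - **Endpoint.** SAP 3.5.1 and Protocol 3.1 define the primary safety endpoint as "incidence, type and causality of SAEs and severe AEs throughout the study period".
- **Collection.** Protocol 8.3.1: "Adverse events will be monitored continuously from informed consent until the last study-related activity". Note n to the schedules in Protocol 8.1 says the same.
- **Nominal length.** The synopsis (Study/Treatment Duration) gives about 10 weeks for two-dose subjects, "including the 6-week safety follow-up period after last administration".
- **Shedding extension.** The same synopsis section says that "if type 2 virus shedding is detected by PCR on one of the last 3 scheduled stool samples, the study duration for this individual" is extended. Further sets of three stools are requested until three in a row are PCR-negative, and that fixes the subject's study end. Protocol 9.1 repeats the rule.
- **Other extensions.** The synopsis and Protocol 9.1 also continue follow-up for unresolved AEs or clinically significant laboratory abnormalities, and ask for a new sample if the last stool is missing. Both rules apply to every arm.
- **Analysis.** SAP 6.5 restricts AE summaries to events from first vaccination onward and sets no end. SAP 6.5.1 applies two-sided Fisher tests to numbers of subjects with an event, Group 5 vs 7 and Group 6 vs 7, post-dose-1, post-dose-2 and overall.
- **Blinding.** Protocol 6.6 (repeated in SAP 3.6): "For the whole study duration all subjects and blinded study staff responsible for safety evaluation of IPV-subjects will not have any information" on what was given. Protocol 8.2.1: "Shedding results for last stool sample will be provided to the sites in a timely manner in order to inform subjects" that more sampling and precautions are needed.

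**The concern.** Groups 5 to 7 form the only randomised, placebo-controlled safety comparison. Placebo recipients should not shed vaccine virus, barring transmission, and Protocol 10.1.3 leaves Group 7 out of the shedding summaries. One of the rules that sets the length of AE collection therefore depends on an effect of the vaccine. A subject-level count with no closing day gives extended vaccinees more time in which to have a first SAE or severe AE. The tilt is against vaccine, and most against the candidate that sheds longest.

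A second issue follows. A subject told of continuing type 2 shedding can infer that vaccine was given, and so can any staff member who sees the result. Causality is part of the primary endpoint and is rated by the investigator.

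**Working it through.** **1. The plan's own figures.** Dose 2 at Day 28 plus 42 days gives Day 70, or 10 weeks, as stated. Nominal post-dose-2 follow-up is 42 days. The 44 per group in Protocol 10.2 is also close to reproduced (6% vs 24%, one-sided 5%: exact power of the Miettinen-Nurminen score test 79.7%). It was set for laboratory elevations, so it says nothing about SAEs or severe AEs.

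**2. Days gained by an extended subject.** Note l to the Protocol 8.1 schedule puts the last three stools at about Day 49 (21 days after dose 2), Days 54-55 and Days 68-69. Results are expected about 21 days after the sample; three stools at one per day then take two further days.

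| Last positive stool | Result known | Three stools end | Gain over Day 70 |
|---|---|---|---|
| Day 49 | Day 70 | Day 72 | 2 days |
| Days 54-55 | Days 75-76 | Days 77-78 | 7-8 days |
| Days 68-69 | Days 89-90 | Days 91-92 | 21-22 days |

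This counts the three weeks from the positive sample. If they run from the final scheduled stool, every row becomes about 21 days. A positive result in an extra round adds roughly another three weeks.

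**3. Effect on the overall comparison.** Assume a constant hazard, equal in both arms, giving 10% by Day 70. A share f of the vaccine arm gains d days.

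- Person-time ratio = (70 + f·d)/70
- Risk in an extended subject = 1 − 0.9^((70+d)/70)
- Arm risk = (1−f)·10% + f·(that risk)

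| f | d | Person-time ratio | Extended subject | Arm (placebo 10%) | Fisher falsely shows vaccine worse, 44 vs 44 |
|---|---|---|---|---|---|
| none | 0 | 1.00 | – | 10.0% | 1.0% |
| 50% | 2 | 71/70 = 1.01 | 10.3% | 10.1% | not run |
| 10% | 21 | 72.1/70 = 1.03 | 12.8% | 10.3% | 1.1% |
| 25% | 21 | 75.25/70 = 1.08 | 12.8% | 10.7% | 1.3% |
| 25% | 42 | 80.5/70 = 1.15 | 15.5% | 11.4% | 1.8% |

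At the minimum of 16 per group, the last column starts at 0.3% and reaches 0.4% (f = 25%, d = 21) or 0.6% (f = 25%, d = 42). The event rate, f and d are assumptions; the documents give none of them.

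**4. Effect on the post-dose-2 comparison.** At the same hazard, 42-day risk is 1 − 0.9^(42/70) = 6.1%. A subject followed 63 days has 1 − 0.9^(63/70) = 9.0%. With f = 25%, the arm has 0.75 × 6.1% + 0.25 × 9.0% = 6.9%, against 6.1% on placebo.

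**5. Why the hazard is generous.** Protocol 1.3.1 reports that severe unsolicited AEs in phase 1 were mostly transient laboratory abnormalities, and Protocol 11.2 makes any laboratory value above grade 1 an AE. The two-dose schedule has its last safety laboratory tests at Day 56, and the extension adds only stools. The main known source of severe AEs is thus largely absent from the extra time, and the excesses in steps 3 and 4 overstate the effect for a given f and d.

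**6. What is untouched.** Solicited events are collected only for Days 0-7 after each dose. In Groups 5 to 7 the post-dose-1 period ends at dose 2, well before any extension.

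**The case against.** The other side is strong on size and scope. Study end also moves for reasons that apply to all arms. Only unsolicited events after dose 2 are exposed. Protocol 10.1.4 treats safety descriptively, and no decision rule hangs on these p-values. The direction is conservative for a safety question, and the AE listing in SAP 6.5.2 shows onset day relative to the preceding dose. All of this stands and keeps the point modest. It does not remove the asymmetry: the arm-neutral rules lengthen follow-up by the same criteria everywhere, whereas the shedding rule does not, and the tabulated rates are tilted whatever the p-value.

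On blinding, Protocol 6.6 provides an unblinded team and promises measures to protect the blinded one, and results go to the sites without saying to whom. A reader might infer that the safety assessors are unblinded. The documents do not say so. What stands is narrower: the extended subject is told, restrictions continue until shedding ends (Protocol 1.3.1), household members may be approached (Appendix 4), and no text keeps the result from the blinded team. The tests of any serious or any severe event do not use causality.

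A cut-off can also do harm if chosen badly. Dose 2 may be postponed by up to 7 days, and a vaccine-related SAE bars it (Protocol 5.4). A single window counted from the last dose would end at Day 42 for a subject who missed dose 2, and could itself depend on a safety outcome. This objection is right and shapes the fix.

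**Conclusion.** The point holds in limited form. As written, ascertainment of unsolicited SAEs and severe AEs depends on allocation in the post-dose-2 and overall comparisons of Groups 5 and 6 with Group 7. The size is probably small: a few days to three weeks or more per extended subject, and in the cases worked above an excess of 0.1 to 1.4 percentage points on a 10% risk, before allowing for the absence of scheduled laboratory tests after Day 56. Fisher's test would rarely be significant because of it, least of all at 16 per group.

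Three stronger readings are tempting:

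- *Only shedding postpones study end, so the whole randomised safety comparison is biased.* The other extensions and the fixed windows contradict this.
- *Every extended subject gains at least 21 days.* This fails if only the Day 49 stool is positive and its result comes back three weeks later.
- *Half an arm gains 42 days, giving 30% more person-time (91/70) and an arm risk of 12.8%.* This would need half the arm still positive about 60 days after dose 2. Phase 1 medians were about 2 and 4 weeks, and the longest duration for candidate 2 was just over a month and a half. Only candidate 1's longest, almost 3 months, reaches that far. The documents give no shedding durations after a second dose, so this comparison is with phase 1 only.

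Separately, notifying a subject of continuing shedding does not fit a blind promised for the whole study, and Protocol 6.6, Protocol 8.2.1 and SAP 3.6 need to be reconciled.

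**What to change.** In SAP 6.5 and 6.5.1, close the comparative AE window for Groups 5 to 7 at a time that does not depend on shedding:

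- **Overall:** a fixed day counted from first vaccination for every subject, whether or not dose 2 was given, for example Day 70 plus the 4-day visit window.
- **Post-dose-2:** 42 days after dose 2, among subjects who received both doses.
- **Later-onset events:** list and tabulate separately as extended follow-up, without a test.
- **SAP Section 7:** record the change, because the protocol endpoint covers the whole study period.

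Two details should be stated. If dose 2 is given at Day 35, its 42-day window ends at Day 77, after a Day 74 overall cut-off; this is acceptable because the rule is the same in each arm. Also, a final visit may fall anywhere from Day 66 to Day 74, so a Day 74 cut-off can leave up to 8 days' difference for an individual, and a Day 70 cut-off up to 4.

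The cost is SAP wording and one extra table. Onset dates are already collected, every late event is still reported, and SAP 6.5 already removes and separately lists data after a non-study vaccine. It would also help to document which staff received PCR results; that does not restore the blind, but it shows which causality ratings could have been affected.
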